7.3 Follow-up Period or Second PK Assessment

7.3.1 *Visit 23 (Day 190)*

- Must occur on the scheduled day
- Required only for subjects participating in the second PK assessment
- AE Assessment

- Concomitant medications
- VS measurements
- Blood samples drawn for:
 - Chemistry (partial panel)
 - Serum 25-hydroxyvitamin D₃, [REDACTED]

7.3.2 *Visit 24 (Day 197)*

- May occur ± 3 day of scheduled day
- Required only for subjects participating in the second PK assessment
- Concomitant medications
- AE assessment
- VS measurements
- Blood samples drawn for:
 - Chemistry (full panel) and hematology
 - Plasma iPTH
 - Serum total 25-hydroxyvitamin D
 - Serum 25-hydroxyvitamin D₃, [REDACTED]

7.3.3 *Visits 25-27 (Days 204-218)*

- Must occur on the scheduled days
- Required only for subjects participating in the second PK assessment
- AE Assessment
- Concomitant medications
- VS measurements
- Blood samples drawn for:
 - Chemistry (partial panel)
 - Serum 25-hydroxyvitamin D₃, [REDACTED]

7.3.4 *Visit 28/ET (Day 225)*

- May occur ± 3 day of scheduled day
- Concomitant medications
- AE assessment
- PE (including weight, height and BMI)
- VS measurements
- 12-lead ECG

- Urine chemistry and urinalysis
- Urine pregnancy (only for females of childbearing potential)
- Blood samples drawn for:
 - Chemistry (full panel) and hematology
 - Plasma iPTH
 - Serum total 25-hydroxyvitamin D
 - Serum 25-hydroxyvitamin D₃, [REDACTED]
 - [REDACTED]

8 QUALITY CONTROL AND ASSURANCE

A quality assurance audit may be performed by the sponsor and/or its designee at selected site(s) to verify that the study was conducted in accordance with the protocol, ICH/GCP, and applicable SOP and regulations, to ensure that the safety and welfare of subjects are addressed, and to confirm that problems reported by study monitors have been resolved. Verification of study documents and study activities (if applicable) will be conducted to confirm accuracy of recorded data and its' analysis. Audit observations and findings will be documented and communicated to appropriate study personnel and management. An inspection may be conducted by regulatory authorities. The investigator must allow direct access to study documents during these inspections and audits.

Monitoring visits will be performed to evaluate study conduct, data integrity, protocol, and GCP compliance and safety.

Each investigator is responsible for the accuracy, completeness, legibility, and timeliness of the data reported. All source documents are to be completed in a neat, legible manner to ensure accurate interpretation of data.

Source documents and laboratory reports will be reviewed to ensure that they are accurate and complete.

9 PLANNED STATISTICAL METHODS

9.1 General Considerations

All analyses will be performed using Statistical Analysis Software (SAS[®]) version 9.3 or higher (SAS[®] Institute, Cary, NC). All data collected on eCRFs and from clinical laboratory evaluations will be grouped and listed by treatment, subject, visit, date and time as feasible. Summary tables will be presented by treatment group where appropriate. Descriptive summaries of categorical outcomes will include the number and percent of subjects. Descriptive summaries of quantitative measures will include the number of subjects, mean, SD, median, minimum, and maximum or as appropriate. In descriptive summary tables, if needed, the geometric mean will be calculated as the n^{th} root of the resulting product of the values, and the coefficient of variation (in percent, %CV) will be calculated as $100^* (\text{SD}/[\text{arithmetic mean}])$.

Arithmetic means, SDs, medians, and geometric means will be reported with the same number of significant figures as the reported values. Minimum and maximum values will be reported with the same accuracy as the reported source data. The %CV will be rounded to one decimal place.

Denominators of percentage of subject calculations will be based on the number of subjects in the treatment group and selected population unless otherwise specified.

In the event there are multiple results at a given visit and/or time point, the following logic will be applied for purposes of summarization by visit or time point: for pre-dose measurements and selection of a baseline value (see [Section 9.4 Definition of Baseline](#)), the more recent non-missing result will be selected; for post-dose measurements, the earliest of the results will be selected. If multiple laboratory results are available for the same date and time and the discrepancy could not be resolved, then the arithmetic mean of the results could be used unless specified in the data management plan or data handling conventions finalized before breaking the study randomization blind. All subjects entered into the clinical database will be included in subject data listings.

For certain analyses, a one-sided familywise type 1 error rate of 2.5% may be appropriately applied. More details will be captured in the Statistical Analysis Plan.

9.2 Determination of Sample Size

Sample size has been calculated (using Fisher's exact test statistics) to provide power of 80% for a two-sided, alpha 0.05 level test of equal proportions comparing the percentages of subjects attaining a mean decrease of at least 30% in plasma iPTH (averaged over the last 6 weeks of treatment) compared to baseline on daily dosages of CTAP101 Capsules (active) versus placebo. Assuming response rates of at least 0.4 (CTAP101 Capsules) versus 0.1 (placebo), and using a 2:1 ratio of CTAP101 Capsules:placebo subjects with an estimated 20% dropout rate over the course of the study, a sample size of approximately 108 subjects is required in the study with two-thirds apportioned to the 12 to <18 year age group (Cohort 1) and one-third apportioned to the 8 to <12 year age group (Cohort 2), allocated as 72 subjects to CTAP101 Capsules and 36 subjects to placebo.

No subject replacement is planned.

9.3 Analysis Populations

9.3.1 Analysis Populations

Efficacy analyses will be conducted for the ITT and PP, as indicated. The ITT population will be defined as all subjects who have been randomized to receive study medication. The PP population will be defined as all subjects who have at least two plasma iPTH determinations included each in the calculated baseline value and in the EAP, defined as weeks 20 through 26 (visits 19-22). Safety analyses will be conducted in the safety population, defined as all randomized subjects who have received at least one dose of the study drug.

9.4 Definition of Baseline

Pretreatment “baseline” will be defined as the last (nearest) non-missing measurement obtained or performed prior to dosing with study drug, unless otherwise stated. Pre-dose measurements obtained or performed at visit 3 are considered as baseline, if available; otherwise measurements on prior visits constitute baseline. Any re-test values for screening visits will be used to calculate baseline in place of original test values obtained on that visit. Definitions of baseline for plasma iPTH and serum calcium, phosphorus, total 25-hydroxyvitamin D and [REDACTED] [REDACTED] will be the average of measurements obtained at Visits 2 and 3.

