Patient reported outcomes on palatability and acceptability.

Sample Size Estimation:

Sample size has been calculated (using Fisher's exact test statistics) to provide power of 80% for a two-sided, alpha 0.05 level test of equal proportions comparing the percentages of subjects attaining mean decreases of at least 30% in plasma iPTH (averaged over the last 6 weeks of treatment) compared to baseline on daily dosages of CTAP101 Capsules versus placebo. Assuming response rates of at least 0.4 (CTAP101 Capsules) versus 0.1 (placebo), and using a 2:1 ratio of CTAP101 Capsules:placebo subjects with an estimated 20% dropout rate over the course of the study, a sample size of approximately 108 subjects is required in the study with two-thirds apportioned to the 12 to <18 year age group (Cohort 1) and one-third apportioned to the 8 to <12 year age group (Cohort 2), allocated as 72 subjects to CTAP101 Capsules and 36 subjects to placebo.

Statistical Analyses:

Efficacy analyses will be performed for the ITT and PP populations, as indicated. The ITT population will be defined as all subjects who have been randomized to receive study medication. The PP population will be defined as all subjects for whom at least two plasma

iPTH determinations are included in the calculated baseline value, defined as weeks -2 through -1, and in the EAP, and who do not have a major protocol deviation.

Primary efficacy will be assessed in the ITT population by comparing the proportions of subjects in each treatment group (CTAP101 Capsules versus placebo) attaining a mean decrease from baseline in plasma iPTH of $\geq 30\%$ in the EAP using the Cochran-Mantel-Haenszel test statistic (alpha=0.05) for overall efficacy of the multicenter results. Subjects who do not have at least two plasma iPTH determinations in the EAP will be deemed non-responders.

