3.3 Study Duration

Each subject will participate in the study for up to approximately 42-weeks (2-weeks screening/baseline, 8-weeks washout, if required, 26-weeks of treatment with CTAP101 Capsules, and 6-weeks of FU evaluation).

Subjects who participate in Cohort 1 will not be eligible for participation in Cohort 2.

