6.9 Appropriateness of Measurements

Reduction in plasma iPTH is an accepted marker for improvement of SHPT in the CKD population. The efficacy of CTAP101 Capsules will be determined by comparing the effect of CTAP101 Capsules to that observed with placebo to lower elevated iPTH levels and to

normalize vitamin D levels. Pre- and postdose averages will be used to minimize the effect of any intrasubject and interassay variability. The post-dose average will be obtained over the last six-weeks of treatment (visits 19-22) to allow subjects to achieve steady state serum 25-hydroxyvitamin D levels.

AEs, serum calcium and phosphorus have been used to assess safety of vitamin D compounds and will be monitored in this study. The safety and tolerability of CTAP101 Capsules will be determined by comparing each active group to placebo.

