7 STUDY ACTIVITIES

7.1 Screening Period

7.1.1 *Visit 1 (Day -70 to -63)*

- AE Assessment
- A signed ICF will be obtained from the subject prior to any study related procedures
- Review of inclusion/exclusion criteria, including eGFR measurement
- Medical history and demographics: date of birth, gender, race, ethnicity, cause and date of CKD. A complete medical history, including alcohol, tobacco and nicotine-containing product use histories and method of contraception, as appropriate, will be recorded
- Medication History: All prescription and over the counter medication usage for the 28 days prior to visit 1 will be recorded
- General PE (including weight, height and BMI)
- VS measurements
- Urine chemistry
- Blood samples to be drawn prior to dosing and washout (if required):
 - Chemistry (full panel) and hematology
 - Plasma iPTH
 - Serum total 25-hydroxyvitamin D
- Urine pregnancy test (only for females of childbearing potential)
- Washout assessment: Subjects who are taking any vitamin D and/or bone metabolism therapy, including vitamin D supplements ($>1,700$ IU/day of ergocalciferol or cholecalciferol), will discontinue or reduce therapy to ≤ 1700 IU/day for the duration of the study. Subjects taking more than 1000 mg/day of elemental calcium will discontinue or reduce therapy for the duration of the study.
 - If washout is not required proceed to visit 3.
 - If washout is required, proceed to visit 2 after completion of at least 8 weeks of washout.

If the screening values do not meet study entry criteria after visit 1, subject may receive supportive care per the investigator's discretion and be retested once. If values do not fall within study entry criteria on retest, the subject will be considered a screen failure and be withdrawn from the study. Only the screening test(s) that did not meet entry criteria at visit 1 are required to be re-drawn and meet entry criteria at the time of the visit 1 retest.

7.1.2 *Visit 2 (Day -7 to -1)*

This visit is only applicable for subjects requiring washout. Subjects requiring washout will need to undergo visit 2 to confirm study entry laboratory values meet or continue to meet study entrance criteria.

- Review of inclusion/exclusion criteria

- Concomitant medications
- AE assessment
- VS measurements
- Blood samples will be drawn for the following analyses:
 - Chemistry (full panel) and hematology
 - Plasma iPTH
 - Serum total 25-hydroxyvitamin D

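### Baseline iPTH is the mean of Visits 2 and 3, but only washout subjects attend Visit 2: as written, no non-washout subject can enter the per-protocol population, and their primary-endpoint baseline is Visit 3 alone or undefined

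*Combined protocol and SAP*

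**What the plan says.** - **Baseline (Section 9.4).** For plasma iPTH, serum calcium, phosphorus and total 25-hydroxyvitamin D (25D), baseline "will be the average of measurements obtained at Visits 2 and 3". For other measures there is a default, the last non-missing pre-dose value: "Pre-dose measurements obtained or performed at visit 3 are considered as baseline, if available". Prior visits count only when Visit 3 is unavailable. A screening re-test replaces the original value.
- **Visit path (Sections 7.1.1 and 7.1.2; Appendix 1, footnote a).** After Visit 1, "If washout is not required proceed to visit 3". Of Visit 2: "This visit is only applicable for subjects requiring washout".
- **PP population (Section 9.3.1).** "The PP population will be defined as all subjects who have at least two plasma iPTH determinations included each in the calculated baseline value", with the same requirement for the efficacy assessment period (EAP).
- **Synopsis, Statistical Analyses.** A different window applies there: "calculated baseline value, defined as weeks -2 through -1".
- **Purpose of averaging (Section 6.9).** "Pre- and postdose averages will be used to minimize the effect of any intrasubject and interassay variability".
- **Screening length.** Section 3.3 allows "2-weeks screening/baseline, 8-weeks washout, if required", while Section 7.1.1 and Appendix 1 place Visit 1 at Day -70 to -63 without distinguishing subjects who skip washout.

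**The concern.** Baseline is the denominator of the primary endpoint, and for one of the two enrolment paths the rule calls for a measurement that is never scheduled.

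Two things follow. First, the PP analyses of iPTH response and of 25D would rest on washout subjects alone. They are a selected group: mainly subjects taken off active vitamin D or calcimimetics, or on high-dose supplements with 25D of at least 30 ng/mL. Second, two programmers could derive different responders in the primary ITT analysis from the same data, one using Visit 3 and the other treating baseline as missing. The non-responder rule in Section 9.10.1 does not settle this, because it covers missing EAP values only.

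**Working it through.** **1. The plan's own sample size.** Inputs from Section 9.2: 0.4 versus 0.1, 2:1 allocation, two-sided 0.05, 80% power, 20% dropout. The continuity-corrected two-proportion formula, which approximates Fisher's test, gives 30 placebo + 60 active = 90, and 90 × 1.2 = 108, as stated. With dropouts counted as non-responders the rates are 0.4 × 0.8 = 0.32 and 0.1 × 0.8 = 0.08. At 72 versus 36, exact Fisher power is 81.3%. The planned size is therefore adequate and does not depend on this point.

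**2. Counting baseline iPTH values.**

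| Path | Scheduled pre-dose iPTH draws | Values in the Section 9.4 baseline | PP minimum |
|---|---|---|---|
| Washout | Visits 1, 2, 3 | 2 (Visits 2, 3) | 2 |
| No washout | Visits 1, 3 | 1 (Visit 3) | 2 |

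No other rule supplies a second value. The last-value default gives way to the specific iPTH rule and would yield only one value anyway. A re-test substitutes for a value and does not add one. The Synopsis window does not help either: Visit 3 is Day 1, so on a strict reading even washout subjects have only one scheduled value in it (Visit 2).

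**3. Size of the PP population and its power.** The washout share w is not in the documents and is assumed. PP size per arm = w × 0.8 × (72 or 36). Power is the sum of the binomial probabilities of all tables that the test rejects at two-sided 0.05, with rates 0.4 and 0.1. The test is the single-stratum Cochran-Mantel-Haenszel (CMH) statistic, with Fisher's test for comparison.

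| w | Active + placebo | CMH power | Fisher power |
|---|---|---|---|
| 25% | 14 + 7 | 26.8% | 15% |
| 50% | 29 + 14 | 52.6% | 46% |
| 75% | 43 + 22 | 77.1% | 71% |
| All completers qualify | 58 + 29 | 87.7% | 85% |

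**4. Effect of one baseline value on the responder call.** The within-subject CV is assumed; the documents give none. Values are simulated as independent lognormal, and response means (mean of 4 EAP values) ÷ (mean of 1 or 2 baseline values) ≤ 0.7.

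| CV | False response, no true change: 1 vs 2 values | Detection of a true 40% fall: 1 vs 2 values |
|---|---|---|
| 15% | 1.4% vs 0.3% | 80.9% vs 87.9% |
| 20% | 4.7% vs 1.8% | 73.6% vs 80.7% |
| 25% | 8.4% vs 4.5% | 68.3% vs 75.2% |
| 30% | 11.9% vs 7.6% | 64.5% vs 71.1% |

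**5. Effect on primary power if Visit 3 alone is used.** The true log-change is taken as normal with an assumed SD of 0.25–0.35, calibrated so that two-value baselines give 0.4 and 0.1. At CV 20–25%, one-value baselines then give 0.394–0.398 and 0.110–0.120. The ITT rate per arm is 0.8 × [w × two-value rate + (1 − w) × one-value rate].

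Example with w = 25% and the milder case: active 0.8 × (0.25 × 0.4 + 0.75 × 0.398) = 0.3188; placebo 0.8 × (0.25 × 0.1 + 0.75 × 0.110) = 0.086. At 72 versus 36 the CMH power is 81.1%.

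Over the whole range, power is 77.5–81.1% (w = 25%), 79.8–82.2% (50%) and 82.1–83.2% (75%), against 84.2% with two values for everyone. The loss is 84.2 − 83.2 = 1.0 to 84.2 − 77.5 = 6.7 points.

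**The case against.** The best case for leaving the plan alone is that the primary endpoint is not really without a baseline. Visit 3 iPTH is drawn for everyone, Section 9.4 already names Visit 3 as the general baseline, and a sensible programmer would fall back on it. That is reasonable, but the text does not say it: the default yields to specific rules and iPTH has one. Even with the fallback, these subjects lose the averaging promised in Section 6.9 and still fail the PP requirement.

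A second argument relies on the Synopsis. If a non-washout Visit 1 falls within two weeks of dosing, and the pre-dose Day 1 draw counts, Visits 1 and 3 provide two values. This shows that the definitions conflict. It does not restore the PP population, because Section 9.4 never uses Visit 1 for iPTH. The related point that Day -70 to -63 may simply describe the full schedule including washout is fair, but the text should say so.

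Several smaller points stand:

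- Footnote a describes washout more broadly, including calcium therapy, so the washout share could be larger than the Section 4.2 criteria suggest.
- No test is named for the PP comparison, and the power depends on the choice, as the table shows.
- PP is secondary, and the 25D endpoint is also analysed in ITT.

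None of these removes the defect.

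**Conclusion.** The point holds and must be fixed. Followed as written, the plan excludes every non-washout subject from PP and leaves their primary-endpoint baseline as Visit 3 alone or unstated. That conclusion follows from the text and needs no assumption.

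The sizes are illustrations. The PP figures depend on the assumed washout share, 20% dropout and the planned response rates. The primary power loss of about 1–7 points depends on the assumed CV, the assumed SD of true change, and the calibration of the planned rates to two-value baselines. Washout status precedes randomization, so the cost to the primary analysis is noise and ambiguity, not bias between arms.

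**What to change.** - **Section 9.4:** define baseline iPTH, calcium, phosphorus and total 25D as the mean of the two latest scheduled pre-dose values: Visits 2 and 3 with washout, Visits 1 and 3 without, using the Visit 1 re-test if one was done. State that a single available value is used if only one exists, and set the maximum interval allowed between the two values.
- **Section 9.3.1 and Synopsis:** refer to that definition and delete the separate weekly window.
- **Sections 7.1.1 and 3.3, Appendix 1:** reconcile the timing of Visit 1 for non-washout subjects. Otherwise the two averaged values could be 9–10 weeks apart.

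The cost is mostly wording, because Visit 1 iPTH, full chemistry and total 25D are already collected. There are small downsides. A Visit 1 value may be older than a Visit 2 value. It may precede a supplement reduction in subjects who reduce without washout. A re-test that had to meet entry criteria is a selected value and subject to regression to the mean. These effects should fall equally on both arms.

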9.5 Demographics Characteristics

Demographic and baseline characteristics will be summarized for the ITT and PP populations by treatment groups separately and combined. Baseline height, weight, BMI, age, sex, race, ethnicity, tobacco and nicotine history, and alcohol history will be tabulated for the safety population.

9.6 Subject Disposition and Withdrawal

Appropriate procedures will be followed, whenever possible, to prevent missing data and to collect the reason for missing data when it does occur, as delineated by [Fleming 2011]. The impact of missing data on the primary efficacy and safety endpoints will be evaluated by sensitivity analyses designed to show how different assumptions about the missing data influence the results. A tipping point analysis will be completed to evaluate the potential effect of further discontinuations and missing data on the study conclusions. These analyses will be detailed in the Statistical Analysis Plan.

Subject disposition will be tabulated and descriptively summarized for all randomized subjects by treatment groups separately and combined. Subject disposition will be summarized by presenting the number and percent of subjects randomized, ITT and PP subjects, subjects who completed study drug administration, subjects who completed the study, and subjects who discontinued prematurely from the study. The primary reason for premature study termination will be detailed together with the number and percent of subjects discontinuing for each reason. The primary reason for premature study termination will be collected from the ET eCRF page and will include the following:

- Occurrence of a SAE or AE
- Disease progression as assessed by clinical judgment and/or objective measurement
- Initiation of dialysis

- Violation of the protocol and/or subject non-compliance
- Lost to FU
- Pregnancy
- Withdrawal of consent at any time, for any reason, at the discretion of the enrolled subject
- Requirement for a 5th reduction in dose
- Other (specific reason)

Screen failure information will be collected regularly by the sponsor. Medical history will be collected on the eCRF at visit 1 and displayed in a data listing as well as summarized by treatment group. Date of diagnoses of CKD and SHPT, stage of CKD, underlying diagnosis of the CKD, and previous and concurrent diseases will be collected in the eCRF and documented on the history of CKD page or as medical history. Medical history events will be sorted alphabetically by System Organ Class (SOC). The coding of the data will be performed with MedDRA version 20.0 or higher, using Preferred Terms (PT).

